9.2 Criteria for the Calculation of Apparent Terminal Elimination Rate Constant and Half-life

The start of the terminal elimination phase for each subject will be defined by visual inspection and generally will be the first point at which there is no systematic deviation from the log-linear decline in concentrations.

The apparent terminal elimination rate constant (λ_z) will only be calculated when a reliable estimate can be obtained using at least 3 data points, preferably not including C_{max}, and the adjusted coefficient for determination of exponential fit (R²-adj) of the regression line is ≥ 0.7 . Parameters requiring λ_z for their calculation (e.g., AUC_(0-∞), t_{1/2}, CL, V_z and V_{dss}) will only be calculated if the R²-adj value of the regression line is ≥ 0.7 . If this rule of r²adj ≥ 0.7 is not respected, this should be well described in the Data Review Report (DRR).

The following regression-related diagnostic PK parameters will be determined, when possible:

Parameter	Units	Definition
λ_z	1/h	apparent terminal elimination rate constant
λ_z Upper	h	end of exponential fit
λ_z Lower	h	start of exponential fit
λ_z N		number of data points included in the log-linear regression
λ_z Span Ratio		time period over which λ_z was determined as a ratio of $t_{1/2}$
R^2 -adj		adjusted coefficient for determination of exponential fit

Where possible, the span of time used in the determination of λ_z (i.e., the difference between λ_z Upper and λ_z Lower) should be ≥ 2 half-lives. If the λ_z Span Ratio is < 2 , the robustness of the $t_{1/2}$ values will be discussed in the Data Review Report (DRR).

9.3 Criteria for Calculation and Reporting of Area Under the Concentration-time Curve

The minimum requirement for the calculation of area under the concentration-time curve (AUC) will be the inclusion of at least 3 consecutive concentrations above the lower limit of quantification. If there are only 3 consecutive concentrations, at least 1 should follow C_{max} . An exception may be made for metabolites, where C_{max} may be the last timepoint.

If the extrapolated area is $> 20\%$, $AUC_{(0-\infty)}$ (and derived parameter i.e. Plasma [^{14}C] - CHF6001) / Total Radioactivity Ratio) may be excluded from the summary statistics at the discretion of the sponsor or pharmacokineticist and should be well described in the Data Review Report (DRR).

9.4 Calculation of $[^{14}C]$ -CHF6001 and $[^{14}C]$ -total radioactivity Urine Parameters

The amount of the dose administered recovered (Ae_u) in urine as $[^{14}C]$ -CHF6001 for each urine collection interval (t_1-t_2) will be calculated as the product of urine concentration and urine volume. Where only urine sample weight is supplied, a specific gravity of 1 g/mL will be assumed, and it will be considered equivalent to urine volume. A total cumulative $Ae_{u\ 0-x\ h}$ will be calculated by summing across collection intervals over the 0-x h interval, where x = end of the last collection time interval.

The percentage of the dose administered recovered in urine over the time interval t_1 to t_2 ($fe_{u\ t1-t2}$) as $[^{14}C]$ -CHF6001 will be calculated for each urine collection interval as follows:

$$fe_{u\ t1-t2} = (Ae_{u\ t1-t2} / dose_{IV}) \times 100$$

Cumulative fe_u (Fe_u) will be calculated by summing the $fe_{u\ t1-t2}$ values across collection intervals in the same manner as cumulative Ae_u .

Renal plasma clearance (CL_R) will be calculated according to the following formula:

$$CL_R = \text{cumulative } Ae_u / AUC_{(0-\infty)_iv}$$

Alternatively, $AUC_{(0-t)}$ may be used if $AUC_{(0-\infty)}$ cannot be reliably calculated following the formula cumulative $Ae_{(0-t)} / AUC_{(0-t)}$, where 't' is the longest common interval with quantifiable concentrations in plasma and urine.

The fraction of the relevant metabolites recovered in urine calculated as amount recovered (Fr_Urine) will be calculated as follows:

$$Fr_{Urine} = (Ar_u / Dose_{IV}) \times 100$$

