#### ***7.2.1.2 Determination of CHF6001 and related analytes in human urine***

Urine samples for total [ $^{14}\text{C}$ ], metabolite profiling (if required) and [ $^{14}\text{C}$ ]-CHF6001 assessment will be collected at pre-dose from -12 hours to immediately before study drug inhaled administration (-12-0h) and at the following time frames relative to the start of the IV from pre-dose infusion: 0-4h, 4-8h, 8-12h, 12-24h, 24-48h, 48-72h, 72-96h, 96-120h, 120-144h, 144-168h, 168-192h, 192-216h and 216-240h, for a total of 14 urine collection intervals.

Subjects will be asked to empty the bladder before both dosing and before the end of each collection interval. All urine voided during the collection intervals will be retained. Access to the toilet will be controlled by the site staff.

Collection and processing are described in the laboratory manual document.

The following time deviations from theoretical post-dose times related to the end of the collection interval will be allowed:

For 4 and 8 hours post-dose	$\pm 10$ min
For 12 and 24 hours post-dose	$\pm 20$ min
For $>24$ hours post-dose	$\pm 30$ min

Longer time deviations will be evaluated on a case by case basis during the Data Review meeting.

**Metabolite profiling:** pooling across timepoints and subjects will be done. This will be followed by chromatography (LC+AMS) and radio-peaks will be detected and quantified. For metabolites in urine and feces (total excreta) accounting for  $\geq 10\%$  of total administered radioactivity structural characterization may be performed, where possible.

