
- $AUC_{0-t}$ : the area under the concentration-time curve from 0 to the last quantifiable concentration will be computed using the linear trapezoidal rule with linear interpolation;
- $AUC_{0-\infty}$ : the area under the concentration-time curve extrapolated to infinity will be calculated as the sum of  $AUC_{0-t}$  and a residual part extrapolated to infinite time. The residual area from the last concentration data point to infinite time is calculated using the approximation:

$$\int_t^{\infty} C_t dt = C_t / \lambda z$$

Where  $\lambda z$  is the first order terminal rate constant, estimated by linear regression of the terminal log-linear segment of the plasma log-concentration curve, and  $C_t$  is the last quantifiable concentration data point. In order to determine  $\lambda z$  by log-linear regression, at least 3 points will be used. The quality of log-linear regression and the reliability of extrapolated PK parameters should be demonstrated by an adjusted coefficient of determination  $R^2$  of at least 0.85;

- $C_{max}$  and  $t_{max}$ : the value and time of the maximum concentration will be obtained directly from the experimental data without interpolation;
- $t_{1/2}$ : the terminal half-life, associated with negative slope ( $-\lambda z$ ), calculated as  $0.693/\lambda z$  from the individual drug concentrations versus time profiles.
- $Dose_{IV}$ : is the actual IV dose calculated as [weight of full syringe (g) minus syringe weight after dose (g)] multiplied by nominal concentration ( $\mu\text{g/g}$ )
- $F_{inh}$ : inhaled absolute bioavailability based on  $AUC_{(0-\infty)}$  for CHF6001 calculated as  $F_{inh} = (AUC_{0-\infty\_inh} \times Dose_{IV}) / (AUC_{0-\infty\_IV} \times Dose_{inh})$ . If  $AUC_{0-\infty}$  is not calculable  $AUC_{0-t}$  will be used.
- $R_{b/p}$ : whole blood to plasma ratio is determined on the [C]-CHF6001 whole blood and plasma concentration ( $C_b$  and  $C_p$ ) 20 min after the start of infusion, calculated as  $R_{b/p} = C_b / C_p$
- $R_{bt/pt}$ : whole blood to plasma ratio is determined on the total-[C] whole blood and plasma concentration ( $C_{bt}$  and  $C_{pt}$ ) 20 min after the start of infusion, calculated as  $R_{bt/pt} = C_{bt} / C_{pt}$
- $CL$ : the total body plasma clearance following IV administration, calculated only for [C]-CHF6001 as  $Dose_{IV} / AUC_{0-\infty}$

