- $CL_{blood}$ : the total body blood clearance following IV administration, calculated only for [C]-CHF6001 as  $CL_{blood} = CL / R_{b/p}$
- $V_{dss}$ : Volume of distribution at steady-state will be calculated only for [C]-CHF6001 as  $Dose_{IV} \times AUMC_{0-\infty} / (AUC_{0-\infty})^2$

Clinical Study Code: CLI-06001AA1-02	Version No.: 1.0
EUDRACT No.: 2020-004201-31	Date: 19 October 2020

- $V_z$ : the volume of distribution during the terminal phase, calculated only for [C]-CHF6001 as  $Dose_{IV}/(AUC_{0-\infty} \times \lambda_z)$
- $Fr_{plasma}$ : fraction of the relevant metabolites in plasma calculated as  $100 \times AUC [^{14}C]\text{-metabolite}/AUC [^{14}C]\text{-total radioactivity}$

The following PK parameters will be calculated, whenever possible, for each subject based on the concentrations of urine [C]-CHF6001 and urine [C]-total radioactivity:

- $Ae_u$ : amount excreted in urine (expressed in weight) over sampling interval calculated as:  $Ae_u = C_{ur} \times V_{ur}$ , where  $C_{ur}$  is the concentration in urine and  $V_{ur}$  is the volume of urine
- Cumulative  $Ae_u$ : cumulative amount excreted in urine, calculated as the sum of the amount excreted in urine for each collection period
- $fe_u$ : percent of the dose excreted in urine over a sampling interval, where  $fe_u = 100 \times (Ae_u/Dose_{IV})$
- $Fe_u$ : cumulative percent of dose excreted in urine, calculated as the sum of the percent of dose excreted in urine for each collection period
- $CL_R$ : renal plasma clearance calculated only for [C]-CHF6001, if plasma  $AUC_{0-\infty}$  is calculable then  $CL_R = \text{Cumulative } Ae_u/AUC_{0-\infty}$ , if Plasma  $AUC_{0-\infty}$  is not calculable then  $CL_R = \text{Cumulative } Ae_u/AUC_{0-t}$ .
- $CL_{R\_blood}$ : renal blood clearance calculated only for [C]-CHF6001, where  $CL_{R\_blood} = CL_R/R_{b/p}$
- $Fr_{urine}$ : fraction of the relevant metabolites recovered in urine calculated as amount recovered ( $Ar_u$ )/ $Dose_{IV} \times 100$

The following PK parameters will be calculated, whenever possible, for each subject based on plasma [C]-CHF6001 and urine [C]-CHF6001 radioactivity:

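### The main renal clearance formula divides urine collected to 240 h at most by plasma AUC to infinity, so CL_R is understated; the SAP's own matched-interval form should be primary

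*SAP*

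**What the plan says.** **Numerator.** Protocol section 8 defines cumulative Ae_u as the "cumulative amount excreted in urine, calculated as the sum of the amount excreted in urine for each collection period". SAP section 9.4 sums over 0 to x h, "where x = end of the last collection time interval". Protocol section 7.2.1.2 ends collection with "192-216h and 216-240h, for a total of 14 urine collection intervals", one of them pre-dose. SAP section 9.6 sets missing or below-quantification urine concentrations to zero when the amount excreted is computed.

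**Main formula.** SAP section 9.4 gives "CL_R = \text{cumulative } Ae_u / AUC_{(0-\infty)_iv". Protocol section 8 gives the same quotient whenever AUC to infinity is calculable.

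**Fallback.** The two documents differ. In protocol section 8, if AUC to infinity "is not calculable then $CL_R = \text{Cumulative } Ae_u/AUC_{0-t", the full cumulative amount is kept, and AUC(0-t) is "the area under the concentration-time curve from 0 to the last quantifiable concentration". In SAP section 9.4 the fallback is Ae(0-t)/AUC(0-t), "where 't' is the longest common interval with quantifiable concentrations in plasma and urine". It is optional and applies only when AUC to infinity cannot be reliably calculated.

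**Related rules.** In SAP section 9.3, when more than 20% of AUC is extrapolated, AUC to infinity "may be excluded from the summary statistics at the discretion of the sponsor or pharmacokineticist"; CL_R is not named there. SAP section 12 declares no departure from the protocol's analysis.

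**The concern.** Renal clearance is the amount excreted over an interval divided by plasma AUC over that same interval. The main formula pairs a truncated amount with an extrapolated AUC. The SAP recognises the principle, since its fallback matches the intervals, but the matched form is the exception and the unmatched form is the default.

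The variables at stake are CL_R and CL_R_blood, both listed PK variables, and E_h_blood, which is computed by subtracting CL_R_blood from CL_blood. Under the main formula CL_R also carries no information beyond CL and Fe_u. In addition, main and fallback values could be pooled in one summary of 8 subjects although they estimate different quantities.

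**Working it through.** The plan states no CL_R, half-life or expected recovery, so there is no figure to reproduce. The check is algebra under linear kinetics with constant renal clearance.

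**Inputs from the documents:** last urine collection 240 h and last plasma 14C sample 240 h from the start of infusion (protocol 7.2.1.1 and 7.2.1.2); CL = Dose_IV/AUC(0-∞); E_h_blood = (CL_blood − CL_R_blood)/Q_H.

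**Assumed:** terminal half-life t½, shown over a range; f, the share of AUC in the terminal phase (f = 1 is the worst case).

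**Step 1. What the main formula estimates.** Ae_u/AUC(0-∞) = (Dose_IV/AUC(0-∞)) × (Ae_u/Dose_IV) = CL × Fe_u, with Fe_u as a fraction.

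**Step 2. Shortfall with urine quantifiable to 240 h.** Since Ae_u(0-240) = CL_R × AUC(0-240), the ratio of reported to true CL_R is AUC(0-240)/AUC(0-∞) = 1 − f × 2^(−240/t½).

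| t½ | Shortfall, f = 1 | Shortfall, f = 0.5 |
|---|---|---|
| 24 h | 0.1% | 0.05% |
| 36 h | 1.0% | 0.5% |
| 48 h | 3.1% | 1.6% |
| 72 h | 9.9% | 5.0% |
| 120 h | 25% | 12.5% |

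At f = 1 the shortfall passes 5% at about 55 h, 10% at about 72 h and 20% at about 103 h.

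**Step 3. Shortfall when urine becomes unquantifiable at u h before 240 h.** Later amounts count as zero, so at f = 1 the shortfall is 2^(−u/t½). For u = 96 h: 2^(−4) = 6% at t½ 24 h and 2^(−2) = 25% at t½ 48 h.

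**Step 4. Which matched interval.** Take t½ 24 h and urine unquantifiable after 48 h:
- Current formula: 1 − 2^(−2) = 0.750 of true CL_R.
- Fixed interval, Ae_u(0-240)/AUC(0-240): 0.750/(1 − 2^(−10)) = 0.751.
- Longest common quantifiable interval (0-48 h): 0.750/0.750 = 1.000.

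A fixed 0-240 h interval therefore does not cure the problem; the SAP's common interval does.

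**Step 5. Protocol fallback.** If urine stays quantifiable to 240 h, the ratio to true CL_R is (1 − 2^(−240/t½))/(1 − 2^(−t_last/t½)). At t½ 24 h and plasma t_last 48 h this is 0.999/0.750 = 1.33. The error is upward, opposite to the main formula.

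**Step 6. Downstream.** CL_R_blood = CL_R/R_b/p has the same relative error as CL_R. For an assumed true renal share of 20% and a CL_R shortfall b, E_h_blood changes by (1 − 0.2(1 − b))/0.8 − 1: +0.75% at b = 3% and +2.5% at b = 10%.

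**The case against.** The strongest reply is that the error may be negligible. With urine quantifiable throughout and a half-life of about 36 h or less, the shortfall is at most about 1%, in a descriptive study of 8 subjects with no test or confidence interval. Nothing in the documents shows a longer half-life. This stands, and it limits the severity.

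A second reply is that controls exist: the SAP's matched fallback, the reliability rules for λz in section 9.2, the 20% extrapolation rule, and a reported %AUCextrap. That percentage bounds the part of the error due to area beyond 240 h when plasma t_last is no later than 240 h. This stands in part. The fallback is optional and the extrapolation rule discretionary. %AUCextrap says nothing about urine set to zero before 240 h. The SAP also accepts an adjusted R² of 0.7 where protocol section 8 asks for 0.85, so more subjects may qualify for the unmatched formula.

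Two stronger readings might be inferred and are not supported:
- *The mismatch biases the reported renal share of elimination.* It does not. Fe_u is amount over dose and contains no AUC. CL_R/CL equals Fe_u because AUC cancels, so any shortfall in it comes from incomplete urinary recovery. Fe_u, Fe_f and their sum address the routes-of-elimination objective directly and are untouched by the mismatch.
- *The protocol's unmatched fallback will be applied.* Protocol section 12.3 leaves the detailed analysis to the SAP, and the SAP replaces that fallback with a matched one. What remains is that SAP section 12 does not declare the change.

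**Conclusion.** The point holds in limited form. The main formula in both documents pairs urine to 240 h at most with AUC to infinity, so CL_R and CL_R_blood are understated, with a small upward effect on E_h_blood when CL_R is a small part of CL. The direction rests on constant renal clearance and a sound λz. The size rests on a half-life that the documents do not give: worst case about 0.1% at 24 h, 3% at 48 h and 10% at 72 h, and more if urine is missing or unquantifiable before 240 h. The difference between the two fallbacks, undeclared in SAP section 12, is a documentary fact that depends on no assumption. Severity is minor unless the half-life is long or urine becomes unquantifiable early.

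**What to change.** 1. In SAP section 9.4 and protocol section 8, define CL_R for every subject as Ae_u(0-t)/AUC(0-t)_iv, with t the longest common interval with quantifiable plasma and urine concentrations. Say how a missing urine collection inside that interval is handled, since section 9.6 would otherwise set it to zero.
2. Keep Ae_u/AUC(0-∞) as a sensitivity value if wanted, labelled as CL × Fe_u.
3. Replace the protocol fallback that divides the full cumulative amount by AUC to plasma t_last.
4. List the changed CL_R definition in SAP section 12.

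The cost is a few lines of text and a partial-area setting in the PK software. No new data are needed: every scheduled urine interval ends at a scheduled plasma sampling time (4, 8, 12 and 24 h, then every 24 h to 240 h). The drawback is that t may differ between subjects, so it should be listed beside each CL_R.

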9.5 Calculation of [¹⁴C]-CHF6001 and [¹⁴C]-total radioactivity Feces Parameters

The amount of the dose administered recovered (Aef) in feces as [¹⁴C]-CHF6001 for each faecal collection interval (t_1-t_2) will be calculated as concentration in faecal collected sample and faecal collected sample weight. A total cumulative $Aef_{0-x\ h}$ will be calculated by summing across collection intervals over the 0-x h interval, where x = end of the last collection time interval.

The percentage of the dose administered recovered in feces over the time interval t_1 to t_2 (fe_{f,t_1-t_2}) as [¹⁴C]-CHF6001 will be calculated for each faecal collection interval as follows:

$$fe_{f,t_1-t_2} = (Aef_{t_1-t_2} / Dose_{IV}) \times 100$$

Cumulative fe_f (Fe_f) will be calculated by summing the fe_{f,t_1-t_2} values across collection intervals in the same manner as cumulative Aef.

The fraction of the relevant metabolites recovered in feces calculated as amount recovered (Fr_feces) will be calculated as follows:

$$Fr_{feces} = (Ar_f / Dose_{IV}) \times 100$$

9.6 Criteria for Handling Below the Limit of Quantification or Missing Concentrations for Pharmacokinetic Analysis

Plasma and whole blood concentrations below the limit of quantification will be reported as BLQ in the concentration and parameters tables. All BLQ values will be considered as 0.00 for pharmacokinetic and descriptive statistical analyses.

All concentration data-points with time deviations outside the permitted ranges (see Table in section 7.2.1.1 and 7.2.1.2 of study protocol) will be excluded from the descriptive statistics on plasma, whole blood and urine concentrations, explained by a footnote in the appropriate tables and figures, but kept in PK parameters estimation unless very large deviations not allowing for a proper calculation of PK parameters are found: these cases will be discussed during the Data Review Meeting and decision will be fully documented in the DRR.

General rules to handle missing PK data are detailed below, but a case by case evaluation will be performed during the DRM in order to properly handle every specific situation (e.g., missing values at time points close to expected t_{max}). Decisions will be fully documented in the DRR.

Rules on how to deal with missing values when deriving PK AUC:

- If intermediate values (not the pre-dose, and not more than 3 consecutive) are missing, they will be considered as missing for the PK analysis and automatically imputed by linear interpolation by Phoenix WNL software.
- If multiple (>1) adjacent values are missing or more than 3 values are missing, then the AUCs will be reported, flagged in the result tables and excluded from the statistical analyses. However, such situations will be discussed case by case at the discretion of the clinical pharmacologist (CP) during the review of the data and fully documented in the DRR.
- If the predose value is missing, then the predose value should be set to “0” for the estimation of the PK parameters. In case of missing predose sample, the Phoenix WNL software will automatically use the value of 0 for the estimation of the PK parameters;
- For an estimation of the urine and stool PK parameters, missing predose value do not affect the final parameter estimates because they are not used in the calculation of A_e .

The following rules apply with special situations defined below:

- If an entire concentration-time profile is BLQ, it will be excluded from PK analysis.
- Where 2 or more consecutive concentrations are BLQ at the end of a profile, the profile will be deemed to have terminated and any further quantifiable concentrations will be set to missing for the calculation of the PK parameters, unless they are considered to be a true characteristic of the profile of the drug.
- If a predose plasma and whole blood concentration is missing, it will be set to 0 by default within Phoenix WNL.

Urine and feces concentrations that are missing or BLQ will be set to zero for the calculation of A_{eu} t_{1-t2} and A_{ef} t_{1-t2} .

